Eligible participants will then be randomized to receive placebo or spironolactone (50 mg/d) for 90 days (Phase I). At the completion of Phase I, participants will undergo repeat end-point assessment followed by a 21-day drug wash out period. Then, the 90 day crossover phase of the trial will occur (Phase II), in which participants randomized to placebo in Phase I will be treated with spironolactone (50 mg/d) in Phase II and *vice versa*. At the conclusion of Phase II, end-point measures are reassessed.

Once all entry criteria have been met and random treatment assignment confirmed, the first dose of study drug 50 mg should be taken by the subject with or without food. Study drug should be taken once daily, preferably in the morning.

Spironolactone/placebo will be dispensed to patients at Brigham and Women's Hospital (BWH) at the time they are having the CPET-Innocor™ at Baseline, Phase 1 and Day 1, Phase II Visits. All drug containers will be returned to BWH at Day 90, Phase I and Day 90, Phase II Visits.

Study drug to be stored at room temperature.

Side effects of spironolactone include headache, diarrhea, cramps, drowsiness, rash, nausea, vomiting, irregular menstrual periods, and irregular hair growth. Fluid and electrolyte imbalance such as hyperkalemia may occur. Gynecomastia may also occur and is related to dose and duration of therapy. It usually reverses upon discontinuation of spironolactone.

VI. Biostatistical Analysis

Endpoints

Study Primary End-points: A two-primary end-point study model¹⁰ will be used in this study, to include change from baseline (study drug day 1) at study drug day 90 for each of the two trial phases in (i) 6 minute walk distance and (ii) peak VO₂ at the completion of exercise as a determinate of overall cardiopulmonary fitness.

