Peak oxygen consumption (pVO₂) is a continuous response variable, and we will be comparing ΔpVO_2 from baseline to 90 days, and baseline to 180 days between control and intervention group. Difference in ΔpVO_2 , from baseline (day 1) to day 90, the treatment effect, will be compared using a 2-sided, paired Student's t test. There are few data on the distribution of change in VO₂ with interventions. Our prior studies, in patients with congenital heart defects, have shown that change in pVO₂ is normally distributed.¹¹ In our observational study of patients with congenital heart disease, those who engaged in frequent activity increased pVO₂ by 1.8 ± 3.2 mL/kg/min. This study included very heterogeneous diagnoses and levels of baseline pVO₂, and we anticipate the variance of the current study to be significantly lower. A true 1.0 mL/kg/min ΔpVO_2 difference would be clinically important. If the true difference in mean response of matched pairs is 1.0 ± 1.7 mL/kg/min, we will need 25 subjects to be able to reject the null hypothesis with probability (power) 0.80

with associated Type I error of 0.05. To account for loss to follow-up or incomplete data, we will enroll 30 subjects. Calculations performed using PS power and sample size program.¹²

Statistical analyses

The proposed strategy for statistical analyses of end-points is illustrated in Figure 2. All end-points will be analyzed by comparing change in outcome from study drug day 1 to study drug day 90. End-points will be summarized descriptively by treatment, and treatment effect will be compared using methods appropriate for a 2x2 crossover design. We do not anticipate substantial carry over effects by placebo or spironolactone on outcome measures due, in part, to the lengthy study drug wash out period.

[figure not shown]

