Figure 3. Stastical ananlysis schema. The CAPS-PAH trial proposes a prospective, randomized, placebo-controlled cross-over design to test the effect of spironolactone therapy on outcome in pulmonary arterial hypertension. In Phase I, patients on stable therapy with ambrisentan (5 -10 mg/d) will be randomized to treatment with placebo or spironolactone (50 mg/d) and testing relevant to the study end-points, such as peak volume of oxygen consumption (pVO_2), will occur at study day 1 and day 90. Following a 21-day drug wash out period, subjects will enter into Phase II of the trial, which is characterized by cross-over to opposite therapy of Phase I. Repeat end-point assessment will be performed at study drug day 1 and study drug day 90 of Phase II. Change in performance on end-points from study drug day 1 at study drug day 90 while receiving spironolactone will be compared to change in

performance from study drug day 1 at study drug day 90 while receiving placebo, using a 2-sided, paired Student's t test. Carryover and period effects will be tested using appropriate methods prior to testing the treatment effect.

VII. Risks and Discomforts

Risks of Spironolactone:

Common Side Effects

- Skin rash
- Headache
- Dizziness
- GI symptoms of nausea, vomiting, gas, diarrhea and stomach pain
- Cramps
- Drowsiness
- Irregular menstrual periods
- Irregular hair growth

Less Common Side Effects

- Hyperkalemia
- Gynecomastia

Risks of the 6- Minute Walk Test:

- Fatigue
- Fainting
- Muscle soreness
- Muscle strain or injury.

Risks of Blood Draws:

- Bruise or pain where the blood samples are taken
- Small risk of infection

- Lightheadedness and/or fainting

Risks of Cardiopulmonary Exercise Test with Innocor™

- Increased dyspnea
- Fatigue
- Muscle soreness
- Chest pain
- Irregular heart beat
- Heart attack which has happened rarely

Participants will be monitored constantly during this test.

VIII. Potential Benefits

Participants may not benefit from taking part in this study.

Potential benefit may be to answer the hypothesis of the current proposal is that the addition of spironolactone (50 mg/d) to selective ET_A inhibition (standard therapy) with ambrisentan (5-10 mg/d) is more effective than standard therapy alone at improving cardiopulmonary fitness and quality of life in patients with PAH.

IX. Monitoring and Quality Assurance

Data Safety Monitoring Plan

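### The plan does not settle its primary analysis: it names a paired t test on change scores with no period term, leaves the promised crossover methods undefined, and probably gives up precision that the scheduled day-1 data could supply

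*Combined protocol and SAP*

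**What the plan says.** Section VI (Endpoints) sets two primary endpoints, 6-minute walk distance and peak VO2. The first is "change from baseline (study drug day 1) at study drug day 90 for each of the two trial phases in (i) 6 minute walk distance"; the same definition applies to peak VO2. Each phase therefore has its own baseline.

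The analysis is described in four places in Section VI that do not fit together:

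- **Statistical Methods, Peak VO2:** the day-1 to day-90 treatment effect "will be compared using a 2-sided, paired Student's t test".
- **Same paragraph:** a further contrast, "baseline to 180 days between control and intervention group".
- **Statistical analyses:** "All end-points will be analyzed by comparing change in outcome from study drug day 1 to study drug day 90", and then "treatment effect will be compared using methods appropriate for a 2x2 crossover design".
- **Legend of the analysis schema (Figure 3):** the paired t test again, now for the endpoints generally, followed by "Carryover and period effects will be tested using appropriate methods prior to testing the treatment effect".

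Drugs and Dosing (Section V) states that the 21-day washout is long enough. Table 1 places Phase II at days 112 to 202 and schedules both primary endpoints at day 1 and day 90 of each phase.

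**The concern.** The paired change-score t test is the only method with a name. It ignores period, and it subtracts the whole day-1 difference whether or not that difference predicts the day-90 difference. If prediction is weak, the subtraction mainly adds noise.

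The crossover methods and the preliminary tests might repair this, but the visible text gives no model, no threshold and no consequence. It does not say whether these methods replace the t test or accompany it. A period or carryover test with no stated consequence is not an adjustment, and it allows the primary analysis to be chosen once the data are known.

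The 180-day contrast adds a third candidate. It is worded as a comparison between groups from one baseline, although each participant receives both treatments and each phase has its own baseline.

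**Working it through.** **Inputs from the plan (Statistical Methods, Peak VO2):** true difference 1.0 mL/kg/min, SD of the paired difference 1.7, two-sided alpha 0.05, power 0.80, 25 evaluable subjects, 30 enrolled. **Assumed, because the documents do not give them:** r, the size of any period shift, any drug residual, and 1:1 allocation to sequence.

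**1. The plan's own figure.** Paired t test, noncentral t: n = 25 gives power 0.806 and n = 24 gives 0.788, so 25 is right. The 95% half-width is 2.064 × 1.7/√25 = 0.70 mL/kg/min.

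**2. Cost of fixing the slope at 1.** Let v be the variance of the within-subject phase difference, taken as equal at day 1 and day 90, and r the correlation between those two differences.

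- Change-score contrast: variance 2v(1 − r).
- Contrast adjusted for the day-1 difference: variance v(1 − r²).
- Ratio: 2/(1 + r).

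Holding the change-score SD at 1.7, the adjusted SD is 1.7 × √((1 + r)/2). With n = 25, a true difference of 1.0 and 22 df:

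| Assumed r | Adjusted SD | Power, noncentral t | Power, simulated with slope estimated | Approx. 95% half-width |
|---|---|---|---|---|
| 0 | 1.202 | 0.98 | 0.97 | 0.50 |
| 0.25 | 1.344 | 0.94 | 0.93 | 0.56 |
| 0.5 | 1.472 | 0.90 | 0.89 | 0.61 |
| 0.7 | 1.567 | 0.86 | 0.85 | 0.65 |

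The simulated column is the fairer one because it counts the cost of estimating the slope. Break-even is near r = 0.9 (0.805 against 0.806), and at r = 0.95 the adjusted contrast is slightly worse (0.794). Simulated type I error was 0.049 to 0.052 for r from 0 to 0.7.

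Here r is not the ordinary test-retest correlation. A subject's stable level cancels from both differences. If the four values are a stable level plus independent visit noise, r is 0 however high the raw correlation.

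**3. Cost of having no period term.** Suppose the change differs between phases by 0.5 mL/kg/min.

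- Near-equal sequences: the SD of the paired differences becomes √(1.7² + 0.5²) = 1.772 and power is about 0.77. With 13 and 12 per sequence, simulation gives 0.76 or 0.80 depending on which sequence is larger.
- All five allowed losses in one sequence (15 against 10): the paired mean moves by 0.5 × 5/25 = 0.10, to 0.90 or 1.10. Paired-t power is then 0.69 or 0.85, the higher value being a product of the bias. With a period term the estimate stays at 1.00 and power is 0.79.
- With no period shift, the period term alone costs almost nothing: 0.804 against 0.806.

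**4. If the washout is incomplete.** Let a spironolactone residual be L1 at Phase II day 1 and L90 at Phase II day 90. With equal sequences the bias is (L1 − L90)/2 for the change score and (r·L1 − L90)/2 for the adjusted contrast. For a true effect of 1.0 and r from 0 to 0.7:

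- L1 = 0.5, L90 = 0: change score 1 + 0.25 = 1.25; adjusted 1.00 to 1 + 0.175 = 1.175.
- L1 = L90 = 0.5: change score 1.00; adjusted 1 − 0.25 = 0.75 to 1 − 0.075 = 0.925.

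Either contrast can be the less biased, so residual effect is not the reason for the change.

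**5. The 180-day contrast.** Two 90-day phases do give 180 study-drug days, but Table 1 ends Phase II at day 202, and no phase-specific baseline lies 180 days before an endpoint.

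**The case against.** The strongest reply is that this is largely a choice between valid analyses. Change from each phase's day 1 is the stated endpoint throughout, the paired t test is named twice, and it matches the sample-size basis. The precision gain depends on an r that nobody has supplied, and at r of 0.9 or more there is none. If a residual lasted to Phase II day 90, the adjusted contrast could understate the effect where the change score would not.

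The period illustration is also an extreme. If five losses fall at random on two sequences of 15, all five land in one sequence with probability 4.2%, while a 3–2 split has probability 67%. A bias of 0.10 is one seventh of the 0.70 half-width. The 180-day phrase may be a matter of labelling. The figures cover peak VO2 only, because the plan gives no effect size or SD for walk distance.

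Most of this stands as a limit on size: the gain is likely, not certain, and the period bias is probably small. None of it answers the pre-specification gap, which does not depend on r. The schema itself is not shown, but its legend survives; it repeats the t test and gives no decision rule.

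**Conclusion.** The concern holds, as something that should be fixed and not as an invalid test or a wrong sample size. The visible text does not say which analysis is primary or what a positive period or carryover test would lead to.

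For peak VO2 at 25 subjects, the adjusted contrast would raise power from 0.81 to between 0.85 and 0.97 for assumed r from 0.7 down to 0. It would narrow the half-width from 0.70 to between 0.65 and 0.50 mL/kg/min. This rests on the plan's SD of 1.7 applying to the change contrast and on equal variances at day 1 and day 90. The possible loss is about 0.01 in power at r = 0.95, plus possible understatement if a residual persists to Phase II day 90.

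**What to change.** For each primary endpoint, name one primary analysis. Regress the within-subject day-90 difference (spironolactone minus placebo) on an order term coded −1/+1, which carries the period effect, and on the uncentred within-subject day-1 difference. The intercept is the treatment effect. In addition:

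- Keep the period term whatever its test shows.
- State that the carryover test is reported descriptively and does not decide the analysis.
- Keep the paired change-score t test as a sensitivity analysis. Disagreement with the primary result would help to show a persisting residual.
- Delete the 180-day contrast or reconcile it with the phase-specific baselines.
- If a mixed model is preferred, split the baseline into subject mean and within-subject deviation. A single phase-specific baseline term is not equivalent. In a check with 400 simulated subjects, phase and within-phase correlations both 0.80, it gave a slope of 0.78 and SE 0.075. The split model and the difference regression both gave a slope of 0.00 and SE 0.059, and the change score SE was 0.084.

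The cost is SAP wording and two degrees of freedom, with no new measurements. Like the paired t test, the model uses only subjects with data from both phases.

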Appendix A

PROCEDURE FOR 6-MINUTE WALK EXERCISE TEST AND BORG DYSPNEA SCALE

General Procedures

The six minute walk exercise test should be administered by the same tester (if possible) and on the same course at each study site throughout the study for a given subject. The administration of the test and specifications of the testing area should be generally consistent with the American Thoracic Society guidelines and the usual practice of the investigative site [ATS guidelines; 2002].

The area used for the six minute walk test should be pre-measured at approximately 30 m in length (but no shorter than 15 m [16 yards or 50 feet] in length at minimum) and at least 2 to 3 m in width. There should be no turns or curves to the six minute walk area. The length should be marked with gradations to ensure the accurate measurement of the distance walked. The area should be well ventilated. The tester may be at the starting end of the corridor or at the midpoint of the corridor with a stop-watch. Intermittent rest periods are allowed if the subject can no longer continue. If the subject needs to rest briefly, he/she may stand or sit and then begin again when he/she is sufficiently rested but the clock will continue to run. At the end of 6 minutes, the tester will call "stop" while simultaneously stopping the watch and then measure the distance walked. The Borg dyspnea rating will be administered immediately following completion of the 6MWT.

Instructions to the Subject

Subjects will be instructed that the preceding meal should be light. Subjects should be told to wear comfortable clothing and sneakers or comfortable walking shoes. The person administering the test will use the following exact dialogue with the subject:

"The purpose of this test is to find out how far you can walk in six minutes. You will start from this point and follow the hallway to the marker (e.g. chair) at the end, turn around and walk back. When you arrive back at the starting point you

will go back and forth again. You will go back and forth as many times as you can in the 6-minute period. You may stop and rest if you need to. Just remain where you are until you can go on again. However, the most important thing about the test is that you cover as much ground as you possibly can during the six minutes. I will tell you the time, and I will let you know when the 6 minutes are up.

When I say STOP, please stand right where you are.”

After these instructions are given to the subject, the person administering the test will then ask:

“Do you have any questions about the test?”

“Please explain to me what you are going to do.”

The person administering the test will then start the test by saying the following to the subject:

“Are you ready?”

“Start when I say “GO.”

The person administering the test will tell the subject the time at 2 and 4 minutes by saying:

“You have completed 2 minutes.”

And then by saying:

“You have completed 4 minutes.”

No other instruction or encouragement will be given during the test. Eye contact with the subject should be avoided during the test.

Following the walk, the person administering the test will obtain a rating of dyspnea using the Borg Scale. The person will use the following dialogue:

"I would like to use the following scale to indicate the maximal shortness of breath you had during the walk test (indicate the Borg Scale). If there was no shortness of breath at all you would point to 0; if the shortness of breath was not very great you would choose from 0.5 to 2; if you were somewhat more short of breath you would select 3; and if the breathing was getting very difficult, you would choose 4 to 9, depending on just how hard it was; 10 represents the greatest shortness of breath you have ever experienced in your life, and if you feel more short of breath than you have ever been in your life before, choose a number greater than 10 that represents how short of breath you feel. If one of the numbers does not exactly represent how short of breath you are, then you can choose a fraction between. For example, if you had shortness of breath somewhere between 4 and 5, you could choose 4 ½.

Appendix B

WHO FUNCTIONAL CLASSIFICATION FOR PULMONARY HYPERTENSION

Class I: Patients with pulmonary hypertension but without resulting limitation of physical activity. Ordinary physical activity does not cause undue dyspnea or fatigue, chest pain, or near syncope.

Class II: Patients with pulmonary hypertension resulting in slight limitation of physical activity. These subjects are comfortable at rest, but ordinary physical activity causes undue dyspnea or fatigue, chest pain or near syncope.

Class III: Patients with pulmonary hypertension resulting in marked limitation of physical activity. They are comfortable at rest. Ordinary activity causes undue dyspnea or fatigue, chest pain, or near syncope.

Class IV: Patients with pulmonary hypertension with inability to carry out any physical activity without symptoms. These subjects manifest signs of right heart failure. Dyspnea and/or fatigue may be present even at rest. Discomfort is increased by any physical activity.

Appendix C

Renal Function Markers	Liver Function Markers	Biochemical Assessments
Creatinine Potassium	AST ALT	Tropoenin-I Collagen III N-terminal procollagen type I IL-6 NT-BNP Aldosterone

Urine pregnancy test will be performed on women of child-bearing age at Phase 1, Day 1 and Phase 2, Day 1

Appendix D**Weight Diary**

Date (Month / Day)	Time (circle AM or PM)	Weight (in lbs)
/	: AM/PM	

Date (Month / Day)	Time (circle AM or PM)	Weight (in lbs)
/	: AM/PM	

Date (Month / Day)	Time (circle AM or PM)	Weight (in lbs)
/	: AM/PM	
NOTES:		

Appendix E

GUIDELINES AND DEFINITIONS FOR RECORDING ADVERSE EVENTS

The Principal Investigator or a designated member of his / her staff will probe each subject for any AEs that may have occurred. The Investigator should always ask the same question when conducting the verbal probe in order to ensure uniformity between subjects. The Investigator should ask:

“How are you doing (feeling)?”

Based on the subject’s response to this question, the Investigator should ask additional questions relevant to the specific complaint such as:

“How severe is/was the symptom?”

“How often did the symptom occur?”

“How long did the symptom last?”

Using provided definitions, the Investigator will then:

(1) rate the intensity and seriousness of the AE, (2) estimate the causality of the AE to study drug, and (3) note actions taken to counteract the AE.

Definitions of Intensity, Seriousness, Causality, Action Taken, and Outcome

INTENSITY

An assessment of the relative intensity (severity) of an AE is based on the Investigator’s clinical judgment. The maximum intensity encountered during the evaluation period should be checked. The assessment of intensity should be independent of the assessment of the seriousness of the AE.

SERIOUSNESS

A serious AE is one that represents an actual or potential significant hazard. This includes, but is not limited to, an event that is fatal, life-threatening, permanently or severely disabling, requires or prolongs inpatient hospitalization, is a congenital abnormality (offspring of subject) or is medically significant (important medical events that may not result in death, be life-threatening, or require hospitalization may be considered a serious AE when, based upon appropriate medical judgment, they may jeopardize the subject and may require medical or surgical intervention to prevent one of the outcomes listed in this definition).

CAUSALITY

An estimate of causality between a specified AE and the study drug is made by the Investigator. Definitions of the categories follow:

- NOT RELATED- there is not a temporal relationship to study drug administration (too early, or late, or study drug not taken), or there is a reasonable causal relationship between another drug, or concurrent disease and the SAE.
- POSSIBLE – there is a reasonable causal relationship between the study drug and the SAE. Dechallenge information is lacking or unclear.
- PROBABLE- there is a reasonable causal relationship between the study drug and the SAE. The event responds to dechallenge. Rechallenge is not required.

ACTION TAKEN

TEST AGENT DOSE MODIFICATION*

- Dose Increased – the dose or regimen of the test agent was increased.
- Dose Not Changed – the dose or regimen of the test agent was not changed.
- Dose Reduced – the dose or regimen of the test agent was decreased.
- Drug Interrupted – administration of the test agent was stopped temporarily
- Drug Withdrawn - administration of the test agent was stopped permanently and not restarted
- Unknown – changes to the administration of the test agent cannot be determined

OUTCOME

- Fatal – The study subject died
- Not Recovered / Not Resolved – The AE was ongoing
- Recovered / Resolved – The AE resolved
- Recovered / Resolved with Sequelae – The AE is considered resolved however there is a residual sequelae.
- Recovering / Resolving – The AE is improving but is not yet completely recovered /resolved
- Unknown – The outcome of the AE cannot be determined.

SERIOUS ADVERSE EVENTS

Medwatch form needs to be completed and faxed to the FDA and a copy sent to [name] (Sponsor of study). Send the Medwatch forms to the attention of [name] [contact]

Medwatch forms can be completed electronically at:

<https://www.accessdata.fda.gov/scripts/medwatch/index.cfm?action=professional.reporting1>

OR

Medwatch form which can be printed from:

<http://www.fda.gov/downloads/AboutFDA/ReportsManualsForms/Forms/UCM163919.pdf>

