Subjects enrolled at Boston Medical Center and Tufts Medical Center will have research biomarker blood samples collected at Brigham and Women's Hospital at Baseline and Day 90 of Phase I, and Days 1 and 90 of Phase II. The research laboratory samples will be collected at BWH when they are here for the Cardiopulmonary Exercise Test (CPET) with Innocor. The samples will be collected at BWH because the research laboratory testing will be performed in [name]'s laboratory. The CPET-Innocor® will be performed prior to Baseline Visit for all subjects enrolled at BWH. Subjects enrolled at BMC and Tufts will have CPET performed after the consent form is signed, but is a clinically indicated procedure.

Approximately 30 mL of blood will be collected

7. Echocardiography

Echocardiography (ECHO) will be assessed at Baseline and Day 90 of Phase I, and Days 1 and 90 of Phase II. The ECHO will evaluate the right ventricle. It is anticipated that by decreasing pulmonary vascular fibrosis to improve pulmonary vascular function, improvements to RV loading will associate with favorable changes to cardiac output, and, consequently, PAH symptomatology.

8. Cardiopulmonary Exercise Test with Innocor™

A previously standardized cardiopulmonary exercise test graded-exercise (CPET) protocol will be used to assess change in non-invasively measured cardiac output and peak oxygen consumption (pVO₂) from baseline (study drug day 1) at study drug day 90 for each of the two trial phases. Refer to Appendix F for description of CPET. All CPET-Innocor required for the protocol will be performed at BWH.

Functional capacity will be assessed per CPET protocol and change in distance on the 6MWT from baseline (study drug day 1) at study drug day 90 for each of the two trial phases.

9. Adverse Events (AE)

AEs will be captured from the time the informed consent form is signed. All AEs should be followed until either resolution (or return to normal or Baseline values), until they are judged by the Investigator to no longer be clinically significant, or for up to 30 days if the AE extends beyond the final visit. All severe AEs (SAEs) should be followed until resolution, death, or the subject is lost to follow-up even if they are ongoing more than 30 days after completion of the final visit. Appendix E provides the guidelines and definitions for recording AEs.

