Each site will be responsible for completing a MedWatch form for all serious adverse events and faxing or e-mailing to the FDA and [name], R.N. for [name]. to review. Refer to Appendix E.

Symptoms of PAH (disease related events) should only be recorded as an AE if the event is either serious, new, or unusual with respect to intensity, frequency, duration as compared to symptoms in the subject's medical history; or there is a reasonable possibility that the event was caused by the study drug.

Inflammatory Biomarker Sub-Study- [REDACTED] Tufts Medical Center Refer Appendix G
6 cc of heparinized blood will be collected and plasma will be obtained.

Time points: Baseline; End of stage 1; End of stage 2.

De-identified samples will be stored at local sites and shipped in batches of 6 samples. Samples will be labeled with unique subject number date and time of collection. Samples to be shipped to [REDACTED] at the following address:

Tufts Medical Center
[name]
[REDACTED]

[name]
[contact]

Tests to be performed from each sample:

- IL-6
- IL-6R
- Gp130
- IL10
- TNF- α
- IL-1 β
- IL-2
- IFN- γ

To measure cytokines, we will use ELISA assay (simple assay or multiplex assays, Bio-Rad)

OVERALL SCHEDULE OF TIMES AND EVENTS (Table 1)

	PHASE I									Wash Out	PHASE II								
	Days 1 - 90										Days 112 - 202								
	1 30 days prior to 1 st dose study drug	3 +/- 3 days	14 +/- 3 days	28 +/- 3 days	42 +/- 3 days	56 +/- 3 days	70 +/- 3 days	90 +/- 5 days	21 days	1 +/- 5 days	3 +/- 3 days	14 +/- 3 days	28 +/- 3 days	42 +/- 3 days	56 +/- 3 days	70 +/- 3 days	90 +/- 5 days		
Telephone Contact		X		X	X		X				X		X	X		X			
Medical History	X																		
Physical Examination (Complex)	X								X		X							X	
Physical Examination (Simple)			X			X							X		X				
Assess Medication Compliance	X		X		X		X			X		X		X		X		X	
SF-36	X								X		X							X	
Other Biochemical Assessment Troponin-I Collagen III N-terminal procollagen type I IL-6	X								X									X	
Inflammatory Biomarkers Sub-study /[name], MD IL-6 IL-6R Gp130 IL10 TNF- α IL-1 β IL-2 IFN- γ	X								X									X	
NT-BNP	X								X		X							X	
Renal function markers (Creatinine/K ⁺)	X		X		X		X		X		X		X		X		X	X	
Liver function markers	X								X		X							X	
6-MWT/Borg Score	X								X		X							X	
Echocardiography	X								X		X							X	
Innocor TM	X								X		X							X	

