 4. IL-6
 5. NT-BNP
 6. Urine pregnancy test for women of child-bearing potential
- CPET-Innocor™
- Assess medication compliance
- Collect all study drug and study drug containers. Study drug will be collected from subjects at BWH.

Drugs and Dosing

The proposed dose of ambrisentan was selected based on retrospective data demonstrating that spironolactone is most effective in combination with ambrisentan at 5 mg/d and 10 mg/d.⁴ The rationale for the proposed spironolactone dose and treatment timing is based on pharmacological studies⁵ and data from clinical trials indicating that 50 mg/d inhibits vascular mineralocorticoid receptor-dependent activity sufficiently in patients with forms of cardiovascular disease relevant to PAH.⁶ We selected a wash out period of 21 days, which is of sufficient duration to extinguish relevant circulating drug levels of this therapy as well as effects of spironolactone on pulmonary vascular function and structure,^{1,2} and is comparable to previously published reports studying the effects of spironolactone on insulin resistance in heart failure⁷ and endothelial function in obesity.⁸

Ambrisentan (a selective endothelin type-A [ETA] receptor antagonist) is an FDA approved treatment for PAH. Participants who qualify to be enrolled in the study are receiving ambrisentan as standard of care for treatment of PAH. Participants must be on a stable dose of ambrisentan (5mg/d – 10 mg/d for >3 mo.). Ambrisentan is taken once daily, preferably in the morning, with or without food.

Spironolactone is a synthetic, steroidal antimineralcorticoid agent with additional antiandrogen and weak progestogen properties, as well as some indirect estrogen and glucocorticoid effects, which is used primarily as a diuretic and antihypertensive, but also for the purpose of reducing elevated or unwanted androgen activity in the body. It acts predominantly as a competitive antagonist of the aldosterone receptor, and belongs to a class of pharmaceutical drugs known as potassium-sparing diuretics. Spironolactone is an FDA approved medication.

The spironolactone tablets provided as 25, 50 or 100 mg strengths.

Placebo tablets are identical in size, shape, and color to spironolactone.

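### Appendix E's causality categories overlap and leave a gap, so the same event can be coded both NOT RELATED and POSSIBLE or PROBABLE, or fit no related category

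*Combined protocol and SAP*

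**What the plan says.** Appendix E (Causality) opens by fixing scope and responsibility: "An estimate of causality between a specified AE and the study drug is made by the Investigator". Three categories follow.

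- The label NOT RELATED has two limbs. The first is that "there is not a temporal relationship to study drug administration (too early, or late, or study drug not taken" (the bracket closes there). The second limb reads "or there is a reasonable causal relationship between another drug, or concurrent disease and the SAE", so the two limbs are alternatives and either one is enough.
- The label POSSIBLE is defined as follows: "there is a reasonable causal relationship between the study drug and the SAE. Dechallenge information is lacking or unclear".
- The label PROBABLE starts from the same link to study drug and adds: "The event responds to dechallenge. Rechallenge is not required".

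No sentence ranks the categories or says what to do when two apply.

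Three other places bear on the point. Section V.9 (Adverse Events) states: "AEs will be captured from the time the informed consent form is signed". The same section limits the recording of PAH symptoms as AEs; one of its routes to recording is that "there is a reasonable possibility that the event was caused by the study drug". Section V (Drugs and Dosing) sets a 21-day washout, "which is of sufficient duration to extinguish relevant circulating drug levels of this therapy as well as effects of spironolactone", by which it means the drug's pulmonary vascular effects.

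**The concern.** A causality scale should give each event one label, and the same label whoever applies the text. This one does not. Two investigators who follow the wording correctly can give opposite codes to the same event. The conflict arises where an event has both a reasonable link to study drug and a reasonable link to something else.

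This trial invites such events. Inclusion criterion 4 requires a PAH diagnosis, and criterion 6 requires stable ambrisentan together with sildenafil or tadalafil. Every participant therefore brings a concurrent disease and at least two other drugs. What is at stake is the consistency of the causality labels, and of any summary of related events later built on them.

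**Working it through.** No arithmetic applies and the plan states no figure to reproduce. The check is a comparison of the definitions.

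**Inputs.** Take events whose timing is compatible with study drug. Let S mean a reasonable causal relationship to study drug, and A a reasonable causal relationship to another drug or a concurrent disease. Dechallenge is unclear (lacking or unclear), positive (the event responds) or negative (it clearly does not respond).

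**Rules as written in Appendix E.**
- NOT RELATED holds whenever A holds, with or without S.
- POSSIBLE is S with dechallenge unclear, with or without A.
- PROBABLE is S with dechallenge positive, with or without A.

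**Result for events where S holds.**

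| A present? | Dechallenge | Labels whose conditions are met |
|---|---|---|
| No | Unclear | POSSIBLE |
| No | Positive | PROBABLE |
| No | Negative | None |
| Yes | Unclear | NOT RELATED and POSSIBLE |
| Yes | Positive | NOT RELATED and PROBABLE |
| Yes | Negative | NOT RELATED only |

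Of the six combinations, two give a single label that reflects the link to study drug. Two give contradictory labels. One gives no label. One gives only NOT RELATED although study drug is a reasonable cause. The table counts logical cases, not expected events.

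**Whether the problem cells can be reached.**
- *Both causes.* Section VII lists dizziness as a spironolactone risk, and Appendix B lists near syncope among PAH symptoms. Section VII also lists hyperkalemia, while exclusion criterion 11 admits patients with creatinine up to 2.0 mg/dL (women) or 2.5 mg/dL (men), so a patient with reduced renal function could have two reasonable explanations for a raised potassium.
- *Negative dechallenge.* Section V (Drugs and Dosing) says gynecomastia usually, not always, reverses after spironolactone is stopped. A case that persists has no related label. Study drug stops at Day 90 of each phase, so any event still present then meets a built-in dechallenge.

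**Scope.** The lead-in covers any specified AE, but all three bullets refer to an SAE. Read by their words, no definition covers a non-serious event.

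**The case against.** The best case on the other side is that these are drafting defects with little consequence. Causality is expressly an investigator's estimate, the lead-in shows that AEs are meant, and little in the trial turns on the label. Much of this stands, and it rules out several stronger readings.

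- *That every event starting in washout is NOT RELATED by rule.* A reader might infer this from the bracketed example about drug not being taken, and might count the 21 days for each spironolactone-first patient as lost. The governing test in that limb is temporal, and the bracket only illustrates it. An event soon after the last dose can still be temporally related. The fair point is that the wording is ambiguous because no post-dose attribution period is given.
- *That any event is open to NOT RELATED because every patient has PAH and takes other drugs.* The text requires a reasonable causal relationship between that disease or drug and the event. Having the disease does not supply one. The documents do not, for example, link gynecomastia to PAH or its treatments.
- *That PAH-like symptoms go unrecorded through Section V.9.* That section has its own reasonable-possibility test, does not refer to the Appendix E categories and has no alternative-cause exclusion. A symptom with both explanations passes it and is recorded. Serious, new or unusual PAH symptoms are recorded in any case.
- *That spironolactone harm is understated or the safety conclusion would change.* General AE capture runs from consent, all SAEs go on a MedWatch form, toxicity events go to the IRB, and creatinine and potassium are measured on schedule, all whatever the label. Attribution is made under double blind, and each patient who completes both phases supplies a placebo period. Section VI plans no analysis that uses a count of related events.

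The objection does not remove the overlap or the gap. These are stated rules that give contradictory labels or none, and investigator judgement cannot settle them because no precedence is given. The SAE wording alone would be editorial.

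**Conclusion.** The point holds in a limited form. The three categories are neither mutually exclusive nor complete, and their wording does not match the AE scope of the lead-in. Some events will have two reasonable explanations, and their labels will be inconsistent or lean toward NOT RELATED.

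The number of affected events cannot be derived from the documents, and no change in the safety conclusion is shown. A comparison of all AEs between spironolactone and placebo periods remains available from the recorded data, although Section VI does not plan one. Efficacy endpoints and sample size are untouched.

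The verdict assumes that the two limbs of NOT RELATED are alternatives, as the word joining them says, and that no instruction outside these documents sets a precedence. The change should be made because the defect is in the rule itself and the repair is cheap.

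**What to change.** Amend the causality definitions in Appendix E and the matching AE form instructions:

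1. Define NOT RELATED as no reasonable possibility that study drug contributed, and state that an alternative cause alone does not qualify.
2. Code an event with both a study-drug and an alternative explanation as at least POSSIBLE.
3. Assign an event with a reasonable study-drug relationship and a negative dechallenge to a named category.
4. Replace SAE with AE in all three definitions.
5. State that not taking study drug at onset does not by itself make an event NOT RELATED when it starts after recent dosing, including in washout.

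Section V.9 needs no change, since it already uses a reasonable-possibility test. The cost is wording and revised form instructions, with no added data. The downside is that more events will be coded possibly related.
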